10.9. PD Analysis

In this trial the blood parasite counts will be evaluated as a pharmacodynamic indicator to derive the systemic parasite clearance rate and thus as an experimental measure of response to treatment. Individual or pooled average (depending on the individual quality of data) parasite clearance rates will be derived using log-linear regression on positive parasite counts. This rate will be correlated to treatment outcome to evaluate the predictive value of this marker for the initial and final treatment outcome. Subsequently, using the developed population PK models, these will be linked in a sequential manner to the pharmacodynamic parasite counts. By following parasite clearance using qRT-PCR and evaluating PK of MF and PM, population PK-PD modeling will enable us to further explore the relationship between drug exposure and parasitological outcome in a more mechanistic way, which can be seen as an essential component in the development of new treatment regimens. Clinical outcome and measures (spleen and liver size), appropriate biochemistry values and other selected biomarkers will also be integrated as possible influential covariates in the PK-PD model, as appropriate. Eventually, the population PK-PD model will be used to identify which PK parameter and/or measure of exposure is critically relating to the rapeutic response for MF and PM, which will be of pivotal value in defining the optimal treatment duration and intensity of MF in future combination regimens.

11. Data Safety Monitoring Board

A Data Safety Monitoring Board (DSMB), composed of a minimum of 3 members including a statistician and a physician all of whom must be independent of the investigator and sponsors, will be set up prior to study initiation. The DSMB will monitor the study in order to ensure that harm is minimized and benefits maximized for the study subjects. All safety and available outcome data will be presented to the DSMB for review. The data and intervals will be agreed prior to the study initiation and documented in the DSMB Charter.

12. Quality Assurance and Quality Control Procedures

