2.1.2. Secondary Objectives

- To assess the safety of two combination regimens of PM (14 days) and MF (14 or 28 days) with the standard 17-day course of SSG-PM
- To describe the efficacy of the PM (14 days) and MF (28 days) investigational arm
- To describe the pharmacokinetic (PK) profiles of PM and MF (14 days and 28 days regimen) in primary VL patients
- To evaluate parasite clearance in each arm as indicated by direct microscopy and quantitative polymerase chain reaction (qPCR)
- To assess the relationship between PK and PD measurements (parasitological and clinical outcome)
- To describe compliance to MF treatment in an outpatient setting

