2.2.2. Secondary Endpoint(s)

Safety:

Frequency of SAEs and AEs requiring treatment discontinuation.

Frequency and severity of adverse events from the start of treatment through the last visit, at D210.

Efficacy:

Initial cure - cure at the end of treatment (Day 28), defined as recovery of clinical signs and symptoms; absence of parasites (microscopy) and no rescue treatment administered up to and including Day 28.

Probable cure - absence of clinical signs and symptoms of VL at D56 and no prior requirement for rescue treatment.

Pharmacokinetics:

Total and partial blood plasma exposure to PM and MF (bioanalysis performed by a validated LC-MS/MS assay), defined as the area under the concentration-time curve, for MF, during treatment and until the last point of follow-up, and for PM based on full curves both on the first day of treatment (day 1) and the last day of treatment (day 14).

Pharmacodynamics:

Blood parasite clearance over time (qualitative and quantitative), as measured by qPCR from blood samples, from baseline until day 210, and at any suspicion of relapse during the trial.

Tissue parasite loads, as semi-quantified by microscopy and qPCR from tissue samples collected at baseline, at the end of treatment (D28) and at any suspicion of relapse during the trial.

 Compliance to MF treatment in an outpatient setting will be described through patients' hospital records history, drug accountability and PK measurements.

3. Study design and study design rationale

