8.4.2. Pharmacodynamic Assessments

Parasite load in blood and tissue aspirate (bone marrow or spleen): PD assessment will be based on real time quantitative polymerase chain reaction (qPCR) for *L. donovani* in EDTA blood or tissue aspirate, based on the amplification of kinetoplastid DNA (kDNA) (other *Leishmania* DNA targets may also be considered), to assess the parasite clearance over time during the treatment with two combination regimen of PM and MF or treatment with SSG/PM.

All patients will have qPCR in tissue and blood at screening and at Day 28 assessment; and during follow-up if there is suspicious of relapse.

In addition, the patients (40 in arm 1 and probably fewer patients in arm 2 now this arm is discontinued) in the intensive cohort who consent to have multiple sampling for PK will also have qPCR blood samples collected at D0, 3, 7, 14, 28, 56 and 210.

Approximately 1 ml EDTA whole blood will be immediately separated from blood EDTA samples taken (e.g. for Complete Blood Count or PK analysis) for the qPCR analysis. The blood samples and also the remainder of bone marrow/spleen aspirate sample (optional) will be immediately diluted with DNA stabilizing buffer solution (L6 buffer) and can then be stored up to 2 years at frozen temperature.

Furthermore, additional relevant PD markers will be considered for analysis in order to monitor treatment effect.

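### Clearance rates are fitted to positive qPCR counts only, so below-detection samples are dropped and, under the log-linear decay the plan assumes, clearance is estimated as too slow

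*Combined protocol and SAP*

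**What the plan says.** The relevant endpoint (section 2.2.2) is "Blood parasite clearance over time (qualitative and quantitative), as measured by qPCR from blood samples, from baseline until day 210", and section 2.1.2 makes parasite clearance in each arm a secondary objective.

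Section 10.9 turns the blood counts into a rate: "parasite clearance rates will be derived using log-linear regression on positive parasite counts". The fit may be individual or a pooled average, according to the quality of a patient's data, with no criterion given. The stated use follows: "This rate will be correlated to treatment outcome to evaluate the predictive value of this marker for the initial and final treatment outcome".

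On sampling, section 8.4.2 says that the intensive cohort "will also have qPCR blood samples collected at D0, 3, 7, 14, 28, 56 and 210", whereas a footnote in section 5.1 restricts D56 and D210 to clinical suspicion of relapse. The intensive cohort is drawn from arms 1 and 2 only. Everyone else, including all of arm 3, has routine blood qPCR only at screening and D28.

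The document states no detection or quantification limit, censoring rule, minimum number of positives, or rule for a patient who turns negative at once.

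**The concern.** A negative result is not missing. It says the load has fallen below a known level, and it is the strongest evidence of fast clearance. Leaving it out selects on the outcome in two ways. Near the limit, only samples that are high by chance, or that come from slow clearers, stay in the regression. A patient with one positive or none gets no slope at all.

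At stake is the assessment of the rate as a predictive marker. If the best responders have no rate and the other rates are shifted, the correlation with outcome is computed in a selected group. A pooled average does not help there, because it gives no patient-level value to correlate.

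**Working it through.** The document gives no figure to reproduce. The check applies the plan's own model at its own sampling days, with assumed values for everything it leaves out.

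**Model.** Log10 load above the limit for patient i on day t is y = b_i - k_i t + error. A sample is positive if y is at least 0.

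**Who can have a slope (no error).** A patient stays positive until day b/k.
- Intensive schedule: positives at D0 and D3 require k < b/3, that is 2/3 = 0.67 log10/day for b = 2 and 3/3 = 1.00 for b = 3.
- Screening and D28 only: k < b/28, that is 2/28 = 0.071 for b = 2 and 3/28 = 0.107 for b = 3.

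**Why pooling is worse.** Take two error-free patients: A with b = 3, k = 0.15; B with b = 2, k = 0.50. A is positive at D0, 3, 7, 14 (3, 2.55, 1.95, 0.90) and B at D0, 3 (2, 0.50). For these six points the mean day is 4.5 and the mean load 10.9/6 = 1.817. Sxy = 35.4 - 6 × 4.5 × 1.817 = -13.65 and Sxx = 263 - 6 × 4.5² = 141.5. The pooled rate is 13.65/141.5 = 0.096, against a mean true rate of (0.15 + 0.50)/2 = 0.325. B leaves the data early, so the late points describe only A.

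**Simulation.** Assumed, not in the document: mean b of 2 or 3 (SD 0.8); mean k of about 0.15, 0.30 or 0.50 (log-SD 0.4); error SD 0.5; days 0, 3, 7, 14, 28; 400 patients, six repeats. Individual fits need at least two positives. The censored fit has a random intercept and slope and uses the probability of lying below the limit for each negative.

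| Mean b | True k | Individual | Pooled | No slope | Censored mixed model |
|---|---|---|---|---|---|
| 2 | 0.146 | 0.123 (-16%) | 0.063 (-57%) | 4% | 0.146 |
| 2 | 0.294 | 0.250 (-15%) | 0.114 (-61%) | 13% | 0.295 |
| 2 | 0.503 | 0.391 (-22%) | 0.204 (-59%) | 34% | 0.516 |
| 3 | 0.150 | 0.143 (-5%) | 0.084 (-44%) | 0.3% | 0.150 |
| 3 | 0.301 | 0.281 (-7%) | 0.142 (-53%) | 2% | 0.303 |
| 3 | 0.506 | 0.458 (-9%) | 0.242 (-52%) | 10% | 0.515 |

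Bias is estimate/truth - 1, for example 0.391/0.503 - 1 = -22%. Least squares with no detection limit returned the true rate (0.293 against 0.294 in the second row), so the loss comes from dropping negatives.

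**Who is lost.** With b = 2, k = 0.5 and error SD 0.4, 62% of the fastest quarter had no slope, against 10% of the slowest. Mean true rate was 0.64 in those dropped and 0.44 in those fitted.

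**Other assumed inputs.** Runs with a common slope (baseline 3-4 log10/mL, limit 0-1 log10) gave 3-14% for individual and 17-44% for pooled fits, with up to 33% having no slope. A further set gave 5-24%, 44-62% and up to 32%, with the censored mixed model within about 6% of truth.

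**Screening and D28 only** (error SD 0.4, k of 0.10 to 0.30). Between 41% and 99.6% of patients had no slope. At k = 0.15 the mean fitted slope was 0.078 to 0.092.

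**Biphasic decay** (k = 0.30 to D7, then 20% of that). The uncensored D0-D28 slope was 0.11. Mean individual positives-only slopes were 0.187 (b = 3) and 0.204 (b = 2), so too fast. Pooled slopes were 0.067 and 0.052, still too slow. The linear censored mixed model gave 0.209 and 0.261, no nearer to 0.11.

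**The case against.** The strongest reply is that this is an experimental marker, that the endpoint is a profile including positive/negative status, and that the slope is only one derivation from it. That limits the weight of the point. It does not repair the rule, because section 10.9 specifies no analysis of negatives. Section 10.8 defers population PK details to a separate plan but does not say that it covers this regression.

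It is also fair that every magnitude is assumed, that bias is only about 3-5% for individual fits when baseline is far above the limit, and that pooling keeps the positive samples of patients who lack a slope. All of this stands. The loss of fast clearers belongs to individual fits, and the larger slope bias to pooled ones.

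A reader might infer four stronger things that the document does not support:
- That the biased slope enters the PK-PD model. Section 10.9 says of the PK models that "using the developed population PK models, these will be linked in a sequential manner to the pharmacodynamic parasite counts". The link is to the counts, and how negatives enter there is not stated.
- That it biases an arm comparison. No between-arm comparison of slopes is specified, arm 2 is descriptive, and arm 3 has no dense sampling.
- That clearance always looks too slow. This holds under log-linear decay; the biphasic runs reverse it for individual fits.
- That a censored model always recovers the truth. It did so when its decay shape was right, and did not under biphasic decay.

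**Conclusion.** The point holds in a limited form. The stated rule discards informative below-detection results. Under the plan's own log-linear model it understates clearance by about 3-24% in individual fits and 17-62% in pooled fits. Individual fits leave 0-34% of intensively sampled patients without a rate, disproportionately the fastest clearers. These ranges rest wholly on assumed loads, rates, limits and assay error; the direction rests on log-linear decay. The rate's planned correlation with outcome is distorted, by an amount not calculated here. The primary non-inferiority test does not use this rate and is unaffected. This is a cheap improvement to a secondary pharmacodynamic analysis.

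**What to change.** Replace the sentence in section 10.9 with a mixed-effects model (random intercept and slope) of log10 load, using all scheduled blood samples from baseline to D28, with negatives left-censored at the stated assay detection limit. The random slope matters: with rates varying between patients, a simple pooled censored fit gave 0.249 against a true 0.325 in one assumed scenario.

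Also:
- Check the log-linear shape, and allow a two-phase decline if it does not fit.
- Report the proportion negative by visit.
- Keep the positives-only fit as a sensitivity check.
- Outside the intensive cohort, including all of arm 3, report change and negativity at D28 rather than an individual positives-only slope. For a patient negative at D28 the change is a lower bound.
- Do not end the fitting window at sustained negativity. A first negative at D28 cannot be confirmed as sustained if later samples are taken only on suspicion of relapse. Sections 5.1 and 8.4.2 should be reconciled on the D56 and D210 samples.

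The cost is revised analysis wording and slightly more programming, with no new samples. The downside is that the model needs the assay limit and a distributional assumption.

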12.1. Investigator's file

The investigator must maintain adequate and accurate records to enable the conduct of the study to be fully documented and the study data to be subsequently verified. These documents include Investigator's Site File, subject clinical source documents and screening / enrolment logs. The Investigator's Site File will contain the protocol/protocol amendments, CRF/SAE and query forms, IEC and regulatory approval with correspondence, sample informed consent, drug accountability records, staff curriculum vitae and authorization forms and other appropriate documents/correspondence etc.

12.2. Case report forms (CRFs)

Data will be collected by laboratory technicians, medical doctors, clinical officers and nurses authorized by the investigator. It will be supervised by the Investigator and signed by the investigator or by an authorised staff member. Study-specific information will be entered into the Case Report Form (CRF) and SAE form (if applicable). Data

Confidential Page 59 of 68

that are derived should be consistent with the source documents or the discrepancies should be explained. All CRF data should be anonymised, i.e. identified by study patient number only.

The investigator at each trial site should ensure the accuracy, completeness, legibility, and timelines of all data reported to the sponsor in the CRFs/SAE forms and any other additional information that is required. The investigator is responsible for keeping all consent forms, screening forms, CRF/SAE form and the completed subject identification code list in a secure location.

12.3. Source documents

The verification of the CRF/SAE form data must be by direct inspection of source documents. Source documents include subject hospital/clinic records, physician's and nurse's notes, appointment book, original laboratory reports, ECG, X-ray, pathology and special assessment reports, signed informed consent forms, consultant letters, and subject screening and enrolment logs.

The investigator must maintain source documents such as laboratory and consultation reports, history and physical examination reports, etc., for possible review and/or audit by DNDi and/or Regulatory Authorities. The Investigator / designee will record the date of each subject's visit in patient file together with a summary of their status and progress in the study.

12.4. Record Retention

The investigator must keep all study documents on file for at least 25 years after completion or discontinuation of the study. After that period of time the documents may be destroyed with prior permission from DNDi, subject to local regulations.

Should the investigator wish to assign the study records to another party or move them to another location, DNDi must be notified in advance.

12.5. Monitoring, audits and inspections

Monitoring visits to the trial site will be made periodically by DNDi representatives or designated clinical monitors to ensure that GCPs and all aspects of the protocol are followed. Source documents and SAE forms/Data clarification forms (DCFs; sent to DNDi pharmacovigilance) will be reviewed for verification of consistency with data on CRFs. The investigator will ensure direct access to source documents by DNDi or designated representatives. It is important that the investigators and their relevant personnel are available during the monitoring visits.

The investigators will permit representatives of DNDi and/or designated clinical monitors to inspect all CRFs/SAE forms/DCFs, medical records, laboratory work sheets and to assess the status of drug storage, dispensing and retrieval at any time during the study. The corresponding source documents for each subject will be made available provided that subject confidentiality is maintained in accord with local regulations. The inspections are for the purpose of verifying the adherence to the protocol and to ensure the study is conducted according to GCP. It is important that the investigators and other trial site staff are available at these visits.

Confidential Page 60 of 68

The monitoring visits provide DNDi with the opportunity to evaluate the progress of the study, verify the accuracy and completeness of CRFs/SAE forms/DCFs, resolve any inconsistencies in the study records, as well as to ensure that all protocol requirements, applicable regulations, and investigator's obligations are being fulfilled. Four visit types are planned: pre-study, study start, during the study, and study end. Visits may also be performed by regulatory authorities.

It will be the clinical monitor's responsibility to inspect the CRFs/SAE forms/DCFs at regular intervals throughout the study, to verify the adherence to the protocol and the completeness, consistency and accuracy of the data being entered on them. The investigator agrees to cooperate with the clinical monitor to ensure that any problems detected in the course of these monitoring visits are resolved.

12.6. Audits and inspections

The trial site may also be subject to quality assurance audits by DNDi or designated representatives and/or to inspection by regulatory authorities or Independent Ethics Committees (IEC).

It is important that the investigators and their relevant personnel are available for possible audits or inspections.

12.7. Data Management

In order to ensure data quality, a uniform hard copy CRF will be designed for use at all the sites. After the CRFs have been completed by the site investigators and monitored by the clinical monitor, they will be collected and sent on an ongoing basis to DNDi data centre, based in Nairobi for data entry (double independent data entry), cleaning and analysis.

CRFs and source documents will be monitored by the clinical monitor. Discrepancies noted either by the monitor or data centre will be queried to the site PI. The trial data will be stored in a computer database maintaining confidentiality in accordance with national data legislation and Good Clinical Practice.

12.8. Confidentiality of trial documents and subjects records

The investigator must assure that subjects' anonymity will be maintained and that their identities are protected from unauthorized parties. On CRFs or other documents submitted to the sponsor, subjects should not be identified by their names, but exclusively by an identification code. The investigator should keep a subject enrolment list showing codes, names, and addresses. The investigator should maintain documents for submission to sponsor authorized representative, and subject's signed written consent forms, in strict confidence.

13. Protocol Amendments

The Principal investigator will ensure that the study protocol is strictly adhered to throughout, and that all data are collected and recorded correctly on the CRF. The Principal investigator may contact the medical coordinator for a protocol waiver for minor deviations from the protocol, e.g. patient unable to attend during visit window.

Confidential Page 61 of 68

All protocol modifications must be documented in writing. Any protocol amendment must be approved and signed by the sponsor and the Principal investigator and is to be submitted to the appropriate IEC for information and approval in accordance with local requirements, and to regulatory agencies if required. Approval by IEC (and Regulatory Authority, if applicable) must be awaited before any changes can be implemented, except for changes necessary to eliminate an immediate hazard to trial subjects, or when the change involves only logistical or administrative aspects of the trial (e.g. change in clinical monitor(s), change of telephone number(s)).

The protocol amendment can be initiated by either sponsor or by any Principal investigator.

The investigator will provide in writing the reasons for the proposed amendment and will discuss with the medical coordinator and sponsor.

14. Early Termination of the Study

Both the sponsor and the investigator reserve the right to terminate the study at any time prior to inclusion of the intended number of subjects, but they intend to exercise this right only for valid scientific or administrative reasons. Should this be necessary, both parties will arrange the procedures on an individual study basis after review and consultation. In terminating the study, the sponsor and the investigator will assure that adequate consideration is given to the protection of the subject's interest.

Reasons for early termination by the sponsor(s) may include but not be limited to:

- Too low enrolment rate.
- Protocol violations.
- Inaccurate or incomplete data.
- Unsafe or unethical practices.
- Questionable safety of the test article.
- Suspected lack of efficacy of the test article.
- Following the recommendation of the DSMB or IEC
- Administrative decision.

Reasons for early termination by the investigator may be:

- Insufficient time or resource to conduct the study
- Lack of eligible patients

In the event that a study is early terminated either by the sponsor or by the investigator, the investigator has to:

Complete all CRFs to the greater extent possible

Confidential Page 62 of 68

- Return all test articles, CRF, and related study materials to the sponsor who provided them
- Answer all questions of the sponsors or their representatives related to data of subjects enrolled at the site prior to study termination
- Ensure that subjects enrolled in the study who had not yet reached a follow up time point are followed up with the necessary medical care.
- Provide in writing the reasons for his decision to the national health authority and the sponsor.

15. Ethics

The experimental protocol for this study has been designed in accordance with the general ethical principles outlined in the Declaration of Helsinki and ICH guidelines for Good Clinical Practice (International Committee for Harmonization). DNDi assures that it will comply with all applicable state, local and foreign laws for protecting the rights and welfare of human subjects. This protocol and any protocol amendments will be reviewed / approved by an IEC before its implementation.

It is the responsibility of the Global or National Coordinating Investigator/Investigator to apply for review to the IEC of the country where the study takes place regarding local rules and regulations. Written approval from all involved IECs must be obtained before implementation of any protocol-specified intervention /investigation provided to the subject (such as subject information sheets or descriptions of the study).

Any modifications made to the protocol after receipt of the IEC approval must also be submitted by the investigator in writing to the IEC in accordance with local procedures and regulatory requirements.

